#### **5.2.2.2 Iron Supplementation**

Excessive blood loss from heavy menses may result in iron deficiency anemia. Iron deficiency anemia is defined by the World Health Organization (WHO) as an Hgb concentration below 12 g/dL (120 g/L) for non-pregnant women. Subjects entering the study with anemia or who develop anemia during the study, if not already taking iron supplements, should be prescribed iron supplementation by the Investigator, as per standard of care. If the Investigator does not prescribe iron supplements for subjects with a Hgb < 12g/dL, the reason should be documented in source documents.

The recommended oral dose of ferrous sulfate is 300 to 325 mg following the diagnosis of anemia. If a subject is unable to tolerate ferrous sulfate then ferrous gluconate, liquid iron or intravenous (IV) iron may be prescribed. If subjects experience constipation from iron supplement use, stool softeners may be prescribed. All iron supplements taken during the study must be recorded on the concomitant medications eCRF.

Further instructions on the provision of iron supplementation and stool softeners will be provided separately from this protocol.

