- LDL-C/HDL-C ratio: ≤ 3 , and > 3
- Total cholesterol/HDL-C ratio: ≤ 4.5 , and > 4.5.

In addition, the number and percentage of subjects who have potentially clinically significant (PCS) lipid values meeting the following criteria any time during the Treatment Period will be summarized by the six analysis groups as in Section 5.3:

- Total cholesterol > 200 mg/dL
- LDL-C > 130 mg/dL
- LDL-C > 160 mg/dL
- HDL-C < 40 mg/dL
- TG > 150 mg/dL
- TG/HDL-C ratio > 3.5
- LDL-C/HDL-C ratio > 4.

Plots will be provided by the four main analysis groups as in Section 5.3 for HDL-C, LDL-C, triglycerides, and hemoglobin during the Treatment Period:

- Final post-baseline lab values vs. Baseline lab values;
- Final post-baseline lab values vs. Baseline lab values for subjects with NCI CTCAE Grade 3 or 4;
- Maximum post-baseline lab values vs. Baseline lab values;
- Maximum post-baseline lab values vs. Baseline lab values for subjects with NCI CTCAE Grade 3 or 4.

Plots will be provided by the four main analysis groups as in Section 5.3 for HDL-C, LDL-C, and triglycerides during the Treatment Period:

• Mean percent change from Baseline in lipid over month.

Post-Treatment Follow-Up Period

All laboratory variables will be summarized with mean, median, standard deviation, minimum, and maximum by the four main analysis groups as in Section 5.3.

Laboratory data collected more than 3 days after the last dose of study drug in the Treatment Period will be included in the summary of data from the Post-Treatment Follow-up Period. Baseline for summaries/analyses in the Post-Treatment Follow-up Period is the same as Baseline for summaries/analyses in the Treatment Period.

In the Post-Treatment Follow-up Period, the following summaries will be presented:

- During the Post-Treatment Follow-up Period, shift tables for change from Baseline to relevant Post-Treatment Follow-up visit(s) according to the normal ranges will be provided for LDL-C, HDL-C, TG, and total cholesterol by the six analysis groups as in Section 5.3.
- During the Post-Treatment Follow-up Period, shift tables for change from Baseline to relevant Post-Treatment Follow-up visit(s) will also be presented

based on the CTCAE grades for LDL-C, HDL-C, TG, and total cholesterol by the four main analysis groups as in Section 5.3.

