Appendix M. Adverse Events of Special Interest

Exceptions to Standard CTCAE Lab Grading Criteria for Elagolix Studies Appendix N.

ANALYTE	GRADE 1 TOXICITY	GRADE 2 TOXICITY	GRADE 3 TOXICITY	GRADE 4 TOXICITY
		HEMATOLOGY		
EOSINOPHIL COUNT INCREASED*	$650 - 1500 \text{ cells/mm}^3$	1501 - 5000 cells/mm ³	$> 5000 \text{ cells/mm}^3$	No Grade 4
HEMATOCRIT DECREASED**	Decrease in > 0% – 5% below LLN or below BL if BL below LLN	Decrease in > 5% - 10% below LLN or below BL if BL below LLN	Decrease in > 10% below LLN or below BL if BL below LLN	No Grade 4
WHITE BLOOD CELL COUNT INCREASED*	10,800 – 15,000 cells/mm ³	> 15,000 - 20,000 cells/mm ³	> 20,000 - 25,000 cells/mm ³	> 25,000 cells/mm ³
		CHEMISTRIES		
BUN**	$1.25 - 2.5 \times \text{ULN}$	$> 2.5 - 5.0 \times ULN$	$> 5 - 10.0 \times \text{ULN}$	$> 10 \times ULN$
LDL CHOLESTEROL HIGH***	130 – 159 mg/dL	$\geq 160 - 189 \text{ mg/dL}$	$\geq 190 \text{ mg/dL}$	No Grade 4
HDL CHOLESTEROL LOW***		Low abnormal: <	: 40 mg/dL***	
PROTEIN, SERUM, LOW*	5.5 - 6.0 g/dL	5.0 - < 5.5 g/dL	< 5.0 g/dL	No Grade 4
* US Department of Health and Human	Services Food and Drug Administ	tration Center for Biologics Evaluation	on and Research. September 27. Gu	uidance for Industry Toxicity

Grading Scale for Healthy Adult and Adolescent Volunteers Enrolled in Preventative Vaccine Clinical Trials.

Elagolix program criteria based on patient population, the disease states under study, and previous clinical trial experience. *

*** National Institutes of Health National Cholesterol Education Program; Detection Evaluation and Treatment of High Blood Cholesterol in Adults (Adult treatment Panel III) Final Report NIH Publication No. 02-5215 September 2002.

quantitative criteria are available. In the CTCAE where similar quantitative values are assigned to multiple grades and a qualitative criterion distinguishes between the grades, the National Cancer Institute's Common Terminology Criteria for Adverse Events (CTCAE) is applied to all hematology and chemistry analytes across the elagolix program where more conservative quantitative grade is applied.

The table above includes those instances where CTAE criteria are not provided for applicable lab parameters and alternative references are applied

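### SAP 12.3.1 plots the maximum post-baseline value for HDL-C and hemoglobin, where low is the adverse direction, so those plots miss transient or partial falls

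*SAP*

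**What the plan says.** SAP 12.3.1 plans a set of Treatment Period plots, by the four main analysis groups, "for HDL-C, LDL-C, triglycerides, and hemoglobin during the Treatment Period". The set has four members, the same for every analyte:

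- "Final post-baseline lab values vs. Baseline lab values";
- that final-value plot again, restricted to women with a CTCAE grade of 3 or 4;
- "Maximum post-baseline lab values vs. Baseline lab values";
- that maximum-value plot again, with the same restriction.

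No plot of a minimum is planned for any analyte.

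The direction of harm is stated elsewhere:

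- **HDL-C.** SAP 12.3.1 lists a value under 40 mg/dL as potentially clinically significant. SAP Appendix N names the abnormality "HDL CHOLESTEROL LOW" and gives it a single low-abnormal category at 40 mg/dL, with no grades. The LDL-C row directly above it is headed as a high abnormality and has Grades 1 to 3.
- **Hemoglobin.** Protocol 5.2.2.2, citing the WHO, defines iron deficiency anemia as an "Hgb concentration below 12 g/dL (120 g/L) for non-pregnant women". The SAP's table of adverse events of special interest lists anemia. A rise in hemoglobin is a secondary efficacy endpoint (SAP 11.3).

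**The concern.** A plot of an extreme value against baseline is useful for safety when the extreme is the adverse one. The maximum serves that purpose for LDL-C and triglycerides. For HDL-C and hemoglobin it shows the best value each woman reached. A woman whose hemoglobin drops and later recovers is plotted at her recovered level, and her final value looks unremarkable too. That course is foreseeable, because Protocol 5.2.2.2 calls for iron to be prescribed to women who develop anemia.

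The Grade 3 or 4 subset adds a second difficulty. If a woman enters the hemoglobin subset because of a severe low value at any time, the maximum plot then shows the value furthest from the one that selected her. If the grade instead refers to the plotted value, a woman whose severe low was transient drops out of the plot. SAP 12.3.1 does not say which is meant. For HDL-C, if Appendix N governs the grading, there is no Grade 3 or 4 to select on, and both the final-value and maximum-value subset plots are empty.

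What is at stake is how well one set of figures shows individual falls in two analytes that belong to the study's safety topics. No test or endpoint depends on these plots.

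**Working it through.** The plan states no figure on this point, so there is none to reproduce. The check is textual, followed by an illustration of size.

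**Text.** The table compares the extreme plotted in SAP 12.3.1 with the adverse direction.

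| Analyte | Extreme plotted | Adverse direction in the documents | Match |
|---|---|---|---|
| LDL-C | maximum | high (SAP 12.3.1, Appendix N) | yes |
| Triglycerides | maximum | high (SAP 12.3.1) | yes |
| HDL-C | maximum | low (SAP 12.3.1, Appendix N) | no |
| Hemoglobin | maximum | low (Protocol 5.2.2.2; anemia as a safety item) | no |

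**Expected extremes.** Protocol Appendix C schedules hematology and the lipid panel at Months 1 to 6, so take six values per woman. Assume independent normal variation around a constant level, with within-woman standard deviation SD. By simulation (400,000 women), the expected maximum of six standard normal values is 1.267 and the expected minimum is −1.266. The gap is 1.267 + 1.266 = 2.53 SD.

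The documents give no within-woman SD. Over assumed ranges:

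- hemoglobin, SD 0.3 to 0.7 g/dL: 2.53 × 0.3 = 0.76 and 2.53 × 0.7 = 1.77, so about 0.8 to 1.8 g/dL;
- HDL-C, SD 3 to 7 mg/dL: 2.53 × 3 = 7.6 and 2.53 × 7 = 17.7, so about 8 to 18 mg/dL.

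Half of each gap, 1.27 SD, is the upward shift of the plotted maximum from the woman's own mean.

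**Which falls each plot would show.** The same simulation used these assumed levels:

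- hemoglobin at 12 g/dL with a fall of 2 g/dL, counted as low at 10.5 g/dL or less;
- HDL-C at 50 mg/dL with a fall of 15 mg/dL, counted as low below 40 mg/dL.

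Falls at one to three visits were placed before the last visit. The ranges run over the assumed SDs.

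| Fall present at | Analyte | Low on maximum plot | Low on final-value plot | Low on minimum plot |
|---|---|---|---|---|
| 1 of 6 visits | Hemoglobin | 0.0% | 0.0–1.6% | 78.0–95.2% |
| 1 of 6 visits | HDL-C | 0.0% | 0.0–7.6% | 84.0–95.3% |
| 3 of 6 visits | Hemoglobin | 0.0% | 0.0–1.6% | 98.7–100% |
| 3 of 6 visits | HDL-C | 0.0% | 0.0–7.7% | 99.0–100% |
| all 6 visits | Hemoglobin | 19.6–74.6% | 76.3–95.2% | 100% |
| all 6 visits | HDL-C | 19.7–74.7% | 76.2–95.3% | 100% |

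The sustained case can be checked by hand. At SD 0.5 g/dL and a level of 10 g/dL, the chance that one value is at or below 10.5 is Φ(0.5/0.5) = Φ(1) = 0.841, which is the final-value result. The chance that all six are is 0.841⁶ ≈ 0.354, against 0.355 simulated for the maximum.

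The maximum plot therefore misses transient and partial falls and shows sustained falls in attenuated form. The percentages depend on the assumed levels and SDs. The direction does not.

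**The case against.** The strongest reply is that low values are well covered elsewhere, and it stands:

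- the companion plots in the same list show the final value against baseline;
- SAP 12.3.1 has normal-range shifts from high or normal to any post-baseline low and to a final low, CTCAE shift tables to the minimum, and listings that flag low values subject by subject;
- HDL-C under 40 mg/dL is summarized at each visit and at any time in the Treatment Period;
- SAP 11.3.4 tabulates hemoglobin change at Months 1 to 6, including a fall of 1.0 g/dL or more, with category shifts at Months 3 and 6;
- anemia is also followed as an adverse event of special interest.

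In addition, Protocol 3.2.2 reports that mean HDL-C rose in the elagolix groups in Phase 2, so a hidden fall in HDL-C is not the average pattern to expect. The hemoglobin half of the point is the stronger one.

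A reader might infer that the SAP hides anemia and HDL-C falls, or makes the safety profile look better than it is. The documents do not support that, because the tables and listings above capture the same low values. What remains is narrower. The tables count women by category, and no planned plot shows a woman's lowest value against her baseline for the two analytes where that is the adverse extreme.

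Two further limits apply. The criticism of the hemoglobin Grade 3 or 4 plot in its sharpest form depends on reading the grade as any-time. The empty HDL-C subset depends on Appendix N governing HDL-C; an empty plot is uninformative but misleads nobody.

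**Conclusion.** The mismatch is real and minor. For HDL-C and hemoglobin the maximum plots in SAP 12.3.1 show each woman's most favourable value, contrary to the adverse direction that the SAP and protocol set themselves. The fault lies in a safety display; the safety analysis still counts low values.

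The size is illustrative only. The gap of about 2.5 SD assumes six independent, normally distributed values around a constant level, and its conversion to g/dL and mg/dL rests on SDs that are not in the documents. That the maximum errs in the favourable direction for these two analytes needs none of those assumptions.

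**What to change.** In SAP 12.3.1:

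- plot the minimum post-baseline value against baseline for HDL-C and hemoglobin, including the hemoglobin Grade 3 or 4 subset;
- keep the maximum for LDL-C and triglycerides;
- for HDL-C, in both the final-value and the extreme-value subset plots, replace Grade 3 or 4 with women who have any on-treatment HDL-C below 40 mg/dL, which is already an SAP criterion;
- state whether Grade 3 or 4 means a grade at any time on treatment or the grade of the plotted value.

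The first and third changes affect five of the sixteen planned displays (four plots for each of four analytes): the two maximum plots for each of HDL-C and hemoglobin, and the HDL-C final-value subset plot. The cost is a small programming and text change, with no new data, test or clinical rule.

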12.3.2 Assessment of Hepatotoxicity

The number and percentage of subjects in each analysis group with maximum on-treatment laboratory values meeting the following criteria compared to the upper limit of normal (ULN) will be summarized by the six analysis groups as in Section 5.3 to assess potential hepatotoxicity.

- ALT \geq 3 × ULN and total bilirubin \geq 2 × ULN
- AST \geq 3 × ULN and total bilirubin \geq 2 × ULN
- ALT and AST \ge 3 × ULN and total bilirubin \ge 2 × ULN
- ALT \ge 3 × ULN and total bilirubin < 2 × ULN
- AST \geq 3 × ULN and total bilirubin < 2 × ULN
- ALT and AST \geq 3 × ULN and total bilirubin < 2 × ULN
- ALT \ge 3 × ULN and total bilirubin \ge 1.5 × ULN
- AST \geq 3 × ULN and total bilirubin \geq 1.5 × ULN
- ALT and AST \ge 3 × ULN and total bilirubin \ge 1.5 × ULN
- $ALT \ge 3 \times ULN, \ge 5 \times ULN, \ge 10 \times ULN, \ge 20 \times ULN$
- $AST \ge 3 \times ULN, \ge 5 \times ULN, \ge 10 \times ULN, \ge 20 \times ULN$
- Total bilirubin $\geq 1.5 \times ULN$, $\geq 2.0 \times ULN$.

The maximum ratio relative to the ULN is used to determine if subjects met the criteria listed above. The ALT, AST, and total bilirubin values do not need to be concurrent in order to meet the defined criteria. For ALT, AST, and total bilirubin, a subject is counted

if the post-baseline laboratory value during the Treatment Period meets the above criteria regardless of Baseline laboratory value (i.e., the post-baseline laboratory value does not need to be worse than Baseline laboratory value).

A listing of all ALT, AST, total bilirubin, and alkaline phosphatase values will be provided for each subject who met any of the criteria defined above.

The following eDISH plots will be generated: peak ASL vs. peak bilirubin; peak ALT vs. peak bilirubin.

12.4 **Bone Mineral Density**

All analyses and summaries of bone mineral density (BMD) will be performed for each segment, i.e., femoral neck, lumbar spine, and total hip. For subjects who had a right-side scan performed (rare instances), their data for right femoral neck and right femoral total hip were included in the analysis with the data for the left femoral neck and left total hip, respectively (available for the majority of subjects), and an additional analysis was performed using the left side only. If more than one scan is reported for an anatomical segment within an analysis window, the worse (the lower value) of the multiple measurements were used for analysis for each anatomical segment.

Unless otherwise specified, summaries will be provided by the six analysis groups as in Section 5 3

12.4.1 **BMD** in the Treatment Period

BMD

A continuous summary of BMD at Baseline, Between Month 3 and Month 6, Month 6, and Final Visit will be provided by analysis group. This summary will include the mean, SD, median, minimum, maximum, and first and third quartiles. This analysis will be repeated excluding subjects who switched machine manufacturer type (Lunar or Hologic), subjects with scans only on Lunar machines, and subjects with scans only on Hologic machines.

The analysis of percent change in BMD from Baseline to each relevant visit in the Treatment Period will be performed. The mean percent change in BMD from baseline to Month 6 and Final Visit during the Treatment Period will be compared between the two elagoix dose groups with at least 12 month of total exposure to elagolix, using ANCOVA with treatment as the main effect and Baseline value of corresponding parameter as a covariate. This analysis will be repeated excluding subjects who switched machine manufacturer type (Lunar or Hologic), subjects with scans only on Lunar machines, and subjects with scans only on Hologic machines. Statistical tests will be two-sided and a significance level of 0.05 will be used.

The number and percentage of subjects with percent change from Baseline to Between Month 3 and Month 6, Month 6, and Final Visit in the Treatment Period in mutually exclusive categories of BMD decrease: $\leq 0\%$, $> 0\% - \leq 1.5\%$, $> 1.5\% - \leq 3\%$, $> 3\% - \leq 3\%$ $\leq 5\%$, > 5% - < 8%, and $\geq 8\%$ will be summarized by analysis group and comparison between the two elagoix dose groups with at least 12 month of total exposure to elagolix will be made using Fisher's exact test.

Z-Score and T-Score

A continuous summary of the Z-score at Baseline, Between Month 3 and Month 6, Month 6, and Final Visit in the extension study will be provided by analysis group. This summary will include the mean, SD, median, minimum, maximum, and first and third quartiles. A categorical summary of Z-score will be summarized at Baseline, Between Month 3 and Month 6, Month 6, and Final Visit for the following categories: ≤ -2.0 , ≥ -2.0 to ≤ -1.5 , ≥ -1.5 to ≤ -1.0 , and ≥ -1.0 for all subjects, subjects with BMD decrease \geq 3% at Month 6, and subjects with BMD decrease < 3% at Month 6, respectively. The categorical summary of worst Z-score at any time in the Treatment Period will be produced by analysis group for each anatomical region.

A continuous summary of the T-score at Baseline, Between Month 3 and Month 6, Month 6, and Final Visit will be provided by analysis group. A categorical summary of T-score will be summarized at Baseline, Between Month 3 and Month 6, Month 6, and

Final Visit for the following categories: ≤ -2.5 , ≥ -2.5 to ≤ -1.0 , and ≥ -1.0 for all subjects, subjects with BMD decrease $\geq 3\%$ at Month 6, and subjects with BMD decrease < 3% at Month 6, respectively. The categorical summary of worst T-score at any time in the Treatment Period will be produced by analysis group for each anatomical region.

Plots will be provided by the four main analysis groups as in Section 5.3 for:

- Percent change from Baseline to Month 6 in BMD vs. Baseline BMD values;
- Percent change from Baseline to Month 6 in BMD vs. Baseline BMD values for subjects with greater than 3% BMD decrease;
- Percent change from Baseline in BMD at Month 6 vs. Baseline Z-score;
- Maximum percent change from Baseline to Post-Baseline in BMD vs. Baseline Z-score;
- Categorical summary of lumbar spine BMD percent change from Baseline to Month 6.

A plot by the four main analysis groups as in Section 5.3 of the cumulative distribution function of percent change from baseline in BMD at Month 6 and the Z-scores at Month 6 will be provided. Additionally, the boxplots of Z-scores at baseline, Month 6, Post-Treatment Month 6, and Post-treatment Month 12 will be provided by the four main analysis groups as in Section 5.3. This will be repeated for T-scores.

Listings of subjects meeting the following thresholds during the Treatment Period in the extension study will be provided:

- Listing of subjects with bone decrease $\geq 8\%$
- Listing of subjects with Z-score ≤ -1.5
- Listing of subjects with T-score ≤ -1.5
- Listing of subjects with Z-score ≤ -1.5 and bone decrease $\geq 8\%$ in the same region
- Listing of subjects with T-score ≤ -1.5 and bone decrease $\geq 8\%$ in the same region.

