11.4 Handling of Multiplicity

No multiplicity adjustment is needed since only summary statistics will be provided for the efficacy analysis.

Safety Analysis 12.0

12.1 **General Considerations**

Safety analyses will be carried out using the Safety Analysis Set, which includes all subjects who received at least one dose of study drug. Safety data will be summarized by actual treatment received. If a subject receives more than one type of study drug, safety data will be analyzed in the treatment group to which she was randomized to. All safety analyses will be based on observed data. For analyses of safety endpoints, subjects who are missing an evaluation will not be included in the analysis of that particular parameter/visit, unless otherwise specified.

For continuous variables, when the analyses of change and/or percent change from Baseline to post-baseline visit(s) are performed, the within-group change from Baseline to each relevant visit will be summarized by analysis group with the mean, SD (or SE), and 95% CIs. The between-group differences of the two elagoix dose groups with at least 12 month of total exposure to elagolix in the Treatment Period will be summarized with the mean, SE, 95% CIs, and P value when applicable. At each post-baseline visit, the Baseline mean and post-baseline visit mean will be calculated for all subjects with baseline and post-baseline value at that visit by analysis group.

For qualitative categorical variables, Fisher's exact test will be used to analyze betweengroup differences when applicable. Categorical data will be summarized by number and percentage of subjects by analysis group.

Pregnancies and outcomes will also be summarized by analysis group.

Statistical comparisons will be performed for BMD between the two elagoix dose groups with at least 12 month of total exposure to elagolix in the Treatment Period, as specified in Section 12.4.1. There will be no testing for other safety endpoints in the Treatment Period. There will be no testing for safety endpoints in the Post-Treatment Follow-up Period.

Information regarding corresponding statistical methods for analyses and any additional statistical measures required for a specific variable/endpoint will be specified in the relevant sections.

12.2 **Adverse Events**

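### SAP 12.4.1 compares six ordered bands of BMD decrease with Fisher's exact test, which ignores the order; an ordinal test would recover power for moderate differences at no cost

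*SAP*

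**What the plan says.** SAP 12.4.1 groups percent change in BMD "in mutually exclusive categories of BMD decrease": 0% or less, above 0 to 1.5%, above 1.5 to 3%, above 3 to 5%, above 5 to below 8%, and 8% or more. For this table the "comparison between the two elagoix dose groups with at least 12 month of total exposure to elagolix" "will be made using Fisher's exact test". The visits listed are the interval between Month 3 and Month 6, Month 6, and Final Visit. No score, trend or rank version is named, and no ordinal test appears elsewhere in the SAP.

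SAP 12.4 adds that BMD analyses "will be performed for each segment, i.e., femoral neck, lumbar spine, and total hip", so the band comparison is run at three sites.

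The same section compares mean percent change at Month 6 and Final Visit "using ANCOVA with treatment as the main effect and Baseline value of corresponding parameter as a covariate", and closes that paragraph with: "Statistical tests will be two-sided and a significance level of 0.05 will be used". The repeats by DXA machine type follow the continuous summary and the ANCOVA; the paragraph on the bands has no such sentence.

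SAP 12.1 gives the general rule: "For qualitative categorical variables, Fisher's exact test will be used", when applicable. It also says that BMD is the only safety endpoint to be tested; SAP 11.1 plans no efficacy tests. Protocol 8.1.8.4 asks only for the bands to be summarized, with no test.

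**The concern.** The bands are ordered cuts of a continuous measurement, and the natural question is whether one group lies further towards large losses. Fisher's exact test on a 2x6 table is a test of general association. Shuffling the six columns leaves its p-value unchanged, so it spreads its sensitivity over every possible pattern of difference, and much of that is wasted when the real difference is a shift along the scale.

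BMD is the only between-group test in the study, and Protocol 3.2.2 and 5.6.1 keep the elagolix-alone arm as a reference for the effect of add-back on bone. The band table shows the tail of the distribution, which a mean does not. At a site where the difference is moderate, a non-significant band test next to a significant ANCOVA would be awkward to explain and could be misread as evidence that the distributions do not differ.

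**Working it through.** **No figure to reproduce.** Neither document states a power or sample size for any BMD comparison. The figure of about 400 subjects (Protocol 8.2, SAP 4.3) is an enrolment expectation and includes former-placebo subjects, who are outside this comparison.

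**Inputs from the documents.** Six bands with cuts at 0, 1.5, 3, 5 and 8%; two-sided 0.05; two groups (SAP 12.4.1). Lumbar spine results at 6 months from Phase 2b (Protocol 3.2.2):

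- Elagolix alone: mean change -3.8% (also given as -3.6%), 25% in the band above 5 to below 8%, 8% at 8% or more.
- Elagolix plus E2/NETA 1 mg/0.5 mg: mean -0.1%, 8.2% in the 3 to 5% band, 2% in the 5 to 8% band, none at 8% or more.

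**Spread implied by those figures**, taking percent change as normal, SD = (cut - mean loss) / z:

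- Alone: 33% lose more than 5%, so (5 - 3.8)/0.440 = 2.73; 8% lose at least 8%, so (8 - 3.8)/1.405 = 2.99.
- With E2/NETA: 10.2% lose 3% or more, so (3 - 0.1)/1.270 = 2.28; 2% lose 5% or more, so (5 - 0.1)/2.054 = 2.39.

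**Assumptions.** The pivotal allocation is not given, so group sizes were varied: 100 vs 200, 133 vs 133, 80 vs 160, 50 vs 100. No hip or femoral neck results are given, so a moderate difference was taken as 0.75, 1.0 or 1.25 percentage points, with common SD 2.7 and a mean loss of 0.5% in the add-back group. Fisher's test was taken as one test on the 2x6 table.

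**Band probabilities.** For mean loss m, P(band k) = Φ((c_k - m)/2.7) - Φ((c_(k-1) - m)/2.7). For the 1.0-point case:

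| Mean loss | ≤0 | >0-1.5 | >1.5-3 | >3-5 | >5-<8 | ≥8 |
|---|---|---|---|---|---|---|
| 0.5% | 42.7% | 21.8% | 17.8% | 12.9% | 4.5% | 0.3% |
| 1.5% | 28.9% | 21.1% | 21.1% | 19.2% | 8.9% | 0.8% |

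**Simulation.** 2,000 trials per moderate or null setting. The Fisher (Freeman-Halton) p-value came from 999 random tables with fixed margins; the comparator was a tie-corrected Wilcoxon test on the same six bands. The last column is the normal-approximation power for the uncategorised change, Φ(d / (2.7 √(1/n1 + 1/n2)) - 1.96). For 100 vs 200 and d = 1.0 this is Φ(1/0.3307 - 1.96) = Φ(1.064) = 85.6%.

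| Groups | Difference | Fisher 2x6 | Wilcoxon | Gap | Uncategorised |
|---|---|---|---|---|---|
| 100 vs 200 | 0.75 | 35.6% | 53.9% | 18.3 | 62.1% |
| | 1.0 | 61.5% | 78.6% | 17.1 | 85.6% |
| | 1.25 | 82.0% | 93.1% | 11.1 | 96.6% |
| 133 vs 133 | 0.75 | 33.0% | 54.5% | 21.5 | 62.0% |
| | 1.0 | 57.2% | 79.6% | 22.4 | 85.5% |
| | 1.25 | 80.5% | 93.6% | 13.1 | 96.5% |
| 80 vs 160 | 0.75 | 28.7% | 44.4% | 15.7 | 52.7% |
| | 1.0 | 51.7% | 72.0% | 20.3 | 77.2% |
| | 1.25 | 72.2% | 87.3% | 15.1 | 92.2% |
| 50 vs 100 | 0.75 | 21.6% | 31.3% | 9.7 | 36.1% |
| | 1.0 | 35.1% | 50.9% | 15.8 | 57.1% |
| | 1.25 | 50.3% | 69.3% | 19.0 | 76.2% |

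The gap runs from 9.7 to 22.4 points (9 to 23 if taken from whole-percent figures). The simulation standard error of each power is at most √(0.25/2000) = 1.1 points.

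**Type I error.** With no difference, Fisher rejected in 4.4 to 5.5% of trials and Wilcoxon in 4.2 to 5.0%, so the gain does not come from a liberal test.

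**Phase 2b-like spine effect** (mean loss 3.8%, SD 2.85, against 0.1%, SD 2.35; 400 trials): both tests had 100% power at every group size.

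**The case against.** The best reply is that the band comparison is secondary. At Month 6 and Final Visit the question of a shift is answered by ANCOVA on the continuous change, which uses more information than any test on bands: about 86% power in the 100 vs 200, 1.0-point example before any gain from the covariate, against 79% for Wilcoxon. Protocol 8.1.8.4 adds a confidence interval for the difference and MMRM as appropriate, and SAP 12.4.1 adds plots of the cumulative distribution. No hypothesis or decision hangs on the Fisher p-value, and a general-association test can pick up differences in shape that are not a shift. All of this stands, and it limits the consequence. It does not make an unordered test the better choice for a table that the SAP has chosen to test at three sites.

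Two further limits also stand. The 2x6 form is an assumption; if one 2x2 test per band is meant, these figures do not apply. And the size of the gap depends on assumed group sizes and differences.

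Some stronger readings are tempting but unsupported:

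- That the weak test is also run in the machine subsets. The repeat sentences belong to the continuous summary and the ANCOVA.
- That the loss is worst for the interval between Month 3 and Month 6. Fisher's is the only between-group BMD test the SAP specifies there, but the scheduled Month 3 scan is limited to subjects with a decrease of 5% or more in spine or total hip at the end of the pivotal study (Protocol 5.3.1.1). The simulation does not describe a set selected in that way, and an ordinal test does not remove the selection.
- That SAP 12.1 is contradicted. Its reference to qualitative variables suggests a poor match with ordered bands, but it is qualified and leaves BMD to 12.4.1.

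**Conclusion.** The point holds as a small, free improvement. The bands are ordered, the planned test ignores the order, and for moderate shifts this costs roughly 10 to 22 percentage points of power against a rank test on the same table, with type I error near 5% for both. That rests on four assumptions: one 2x6 test, groups between 50 vs 100 and 133 vs 133, differences of 0.75 to 1.25 points, and normal percent change with SD 2.7.

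A reader might infer that the study could miss the effect of add-back on bone. The documents do not support that. At the only documented effect, the Phase 2b spine difference of about 3.7 points, neither test loses anything, and ANCOVA carries the main comparison. Whether hip and femoral neck differences fall in the moderate range cannot be told from these documents.

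**What to change.** In SAP 12.4.1, replace Fisher's exact test for the six bands with a tie-corrected Wilcoxon rank-sum test or a CMH row-mean-score test, in an exact version where counts are sparse. If a test of the extreme tail is wanted, keep Fisher's test for a single cut such as a decrease of 8% or more, and say that it is a 2x2 comparison. State that ANCOVA on the continuous percent change is the main between-group BMD comparison and that the band test supports it.

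The cost is one line of the SAP. It needs no new data or tables, and no protocol amendment, because Protocol 8.1.8.4 asks only for the bands to be summarized.
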